#### **4.2.2 Safety laboratory data**

Measurements below the limit of quantification (BLQ) will be imputed with half of the lower limit of quantification (LLOQ) for the purpose of calculating change and percentage change from Baseline for summaries and figures. Measurements above the limit of quantification (ALQ), if applicable, will be imputed to the upper limit of quantification.

Descriptive statistics will be calculated if at most 33% of the individual data points at a time point are missing or are either not quantifiable (<LLOQ) or ALQ. If no participants have data at a given time point, then only n=0 will be presented. If n<3, then only the n, minimum and maximum will be presented. If n=3, then only n, minimum, median and maximum will be presented. The other descriptive statistics will be left blank.

#### **4.2.3 Anti-drug antibody data**

Levels of ADAb that are BLQ will be regarded as missing for all individual ADAb figures.

#### **4.2.4 Dates and times**

Partial dates/times may be imputed for the following reasons:

- Classification of AEs as treatment-emergent
- Classification of medications as prior or concomitant

Imputed dates/times will not be shown in the listings; all dates will be displayed as reported in the database.

The following rules will be applied for partial start dates/times:

- If only the start month and year are specified, and these are not the same as the month and year of dosing then use the 1st of the month, or the date of Screening if this is later (if the latter imputation results in an end date that is earlier than the start date, then use the 1st of the month). If time is missing this will be imputed as 00:00 h;
- If only the start month and year are specified, and the month and year of dosing are the same as the month and year of the start date, then use the date of dosing. If this results in an imputed start date that is after the specified end date, then use the 1st of the start month, or the date of Screening if this is later (if the latter imputation results in an end date that is earlier than the start date, then use the 1st of the month). If the imputed date is the date of dosing then time will be imputed as the start time of the sc injection (i.e., event will be regarded as treatment-emergent);
- If only the year is specified, and the year of dosing is not the same as the year of the start date then use January 01 of the year of the start date. If time is missing this will be imputed as 00:00 h;
- If only the year is specified, and the year of dosing is the same as the year of the start date, then use the date of dosing. If this results in an imputed start date that is after the specified

end date, then use January 01 of the year of the start date, or the date of Screening if this is later (if the latter imputation results in an end date that is earlier than the start date, then use January 01). If the imputed date is the date of dosing then time will be imputed as the start time of the sc injection (i.e., event will be regarded as treatment-emergent);

- If the start date is completely unknown, then use the date of dosing. If this results in an imputed start date that is after the specified end date, then use January 01 of the year of the end date, or the date of Screening if this is later (if the latter imputation results in an end date that is earlier than the start date, then use January 01). If the imputed date is the date of dosing then time will be imputed as the start time of the sc injection (i.e., event will be regarded as treatment-emergent).

Any medication with a start date on the dosing date and time unknown, will be assumed to be concomitant.

The following rules will be applied for partial stop dates:

- If only the month and year are specified, then use the last day of the month;
- If only the year is specified, then use December 31 of the known year;
- If the stop date is completely unknown, do not impute the stop date.

Missing or partially missing date and/or times will be imputed as described in [Table 4-1](#) for the calculation of duration of each AE. Adverse event duration is computed and reported in day and time format: xx d hh:mm.

**Table 4-1: Calculation rules for duration (days) of AEs (applicable also to ADEs)**

Data Availability	Onset Date/Time	Outcome Date/Time	Calculation Rules
Complete data	D1/T1	D2/T2	$\text{Duration} = [(D2 - D1) * 24 + (T2 - T1)]/24 \text{ d}$
End time missing	D1/T1	D2/--	End time is substituted by time 23:59h (=23.98 in decimal format). $\text{Duration} = < [(D2 - D1) * 24 + (23.98 - T1)]/24 \text{ d}$
Start time missing	D1/--	D2/T2	Onset time is substituted by 00:00h. $\text{Duration} = < [(D2 - D1) * 24 + T2]/24 \text{ d}$
Start and end time missing	D1/--	D2/--	$\text{Duration} = < (D2 - D1) + 1$
Start day and time missing	--/--	D2/T2	$\text{Duration} = < [(D2 - D0) * 24 + (T2 - T0)] / 24 \text{ d}$ For a participant in the FAS, D0 and T0 are the date and time of dosing and for screen failures, D0 = the Screening Visit date and T0 = 0.

**Table 4-1: Calculation rules for duration (days) of AEs (applicable also to ADEs)**

Data Availability	Onset Date/Time	Outcome Date/Time	Calculation Rules
End day and time missing	D1/T1	--/--	For ongoing AE duration = > Discharge day – D1 d For resolved AE duration = < Discharge day – D1 d Where Discharge Day refers to the date of the SFU visit or date of discontinuation.  For any AEs with known start date/time after the date of discontinuation, the date of last contact will be used as the discharge day.
Start and end date missing	--/--	--/--	For ongoing AE duration = > Discharge day – D0 d For resolved AE duration = < Discharge day – D0 d Where Discharge Day refers to the date of the Safety Follow-Up visit or date of discontinuation. For a participant in the FAS, D0 is the date of dosing and for screen failures, D0 = the screening visit date.

ADE=Adverse Device Effect; AE = Adverse Event; FAS=Full Analysis Set

#### 4.2.5 Impact Of COVID 19

The FDA and EMA (see REFERENCES) have provided guidance to help assure the safety of study participants, maintaining compliance with good clinical practice (GCP), and minimizing risks to study integrity during the COVID-19 pandemic. At the time of writing, the impact of the pandemic is still evolving and regulators continue to clarify their position. One of the recommendations is a risk assessment of the impact of COVID-19 on study integrity and interpretability of potential study results. In particular, the major statistical principles that need to be considered when considering the impact of COVID-19 on studies and how to handle missing or delayed assessments resulting from the pandemic. The impact of the COVID-19 pandemic, at the visit level, will be assessed by data collected on a specific COVID-19 impact CRF. Drop outs due to COVID-19 will be handled in the same way as drop out for other reasons. Should one of the ongoing reviews of COVID-19 related PDs (see Section 3.4) suggest that the impact of COVID-19 is more significant than expected e.g. in the case of a second wave, the SAP may be updated to include details of strategies to handle missing data and/or sensitivity analyses.

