#### **8.3.1 Time period and frequency for collecting AE and SAE information**

All AEs and SAEs will be collected from the signing of the ICF and at the time points specified in the schedule of activities (Section 1.3).

In order to ensure complete safety data collection, all AEs occurring during the study (ie, after the signing of the ICF), including any pretreatment and posttreatment periods required by the protocol, must be reported in the CRF even if no study medication was taken but specific study procedures were conducted. This includes all AEs not present prior to the initial visit and all AEs that recurred or worsened after the initial visit.

All SAEs will be recorded and reported to the Sponsor or designee within 24 hours, as indicated in Appendix 4 (Section 10.4). The Investigator will submit any updated SAE data to the Sponsor within 24 hours of it being available.

The Investigator is specifically requested to collect and report to UCB (or its representative) any SAEs (even if the Investigator is certain that they are in no way associated with the IMP), up to 30 days from the end of the study for each study participant, and to also inform study participants of the need to inform the Investigator of any SAE within this period. Serious AEs that the Investigator thinks may be associated with the IMP must be reported to UCB regardless of the time between the event and the end of the study.

The method of recording, evaluating, and assessing causality of AE and SAE and the procedures for completing and transmitting SAE reports are provided in Appendix 3 (Section 10.3).

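### For dosed participants, SAP Table 4-1 counts AE duration from dosing when the start date is missing, so the AE listing can show negative durations and false or unsupported bounds

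*SAP*

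**What the plan says.** SAP 4.2.4 contains two sets of rules for incomplete AE dates.

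The first set imputes partial start dates in order to classify AEs as treatment-emergent and medications as prior or concomitant. It uses a known month where there is one. For a completely unknown start it imputes dosing, with a fall-back: "If this results in an imputed start date that is after the specified end date, then use January 01 of the year of the end" of the AE. Screening replaces that January day when it comes later.

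The second set is Table 4-1, which governs duration. It is introduced with "Missing or partially missing date and/or times will be imputed as described in" the table. Three of its outputs matter here:

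- **Start missing, end known.** The duration is printed with a less-than sign and counted from D0/T0. The anchor for dosed participants is given as "For a participant in the FAS, D0 and T0 are the date and time of dosing". A different anchor applies to those never dosed: "for screen failures, D0 = the Screening Visit date and T0 = 0".
- **Start and end missing, AE ongoing.** The row reads "For ongoing AE duration = > Discharge day – D0 d".
- **Start and end missing, AE resolved.** Here the sign changes: "For resolved AE duration = < Discharge day – D0 d".

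In the two both-missing cases D0 is the dosing date alone for dosed participants, and discharge is the safety follow-up visit or the date of discontinuation. The table has no condition that the end falls on or after D0.

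Protocol 8.3.1 states: "All AEs and SAEs will be collected from the signing of the ICF". SAP 11.2 likewise records AEs from informed consent, and SAP 3.2.2 places Screening on Day -28 to Day -2. Protocol 9.5.1 and SAP 11.2 both require the duration of AEs in a listing. The SAP listing covers all AEs and only flags the treatment-emergent ones.

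**The concern.** Dosing is not the earliest possible onset of an AE in this study, because collection starts up to four weeks before it. A duration counted from dosing and printed as an upper bound is therefore safe only if the AE is known to have started after dosing, and in these rows the start is unknown. The table treats screen failures differently, so pre-dose AEs were foreseen, but it makes no provision for them in participants who were later dosed.

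The ongoing row has a different problem. When the onset is known, discharge minus onset is a proper minimum for an AE that has not ended. When the onset is unknown and dosing is put in its place, the minimum has no basis in the record.

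At stake is the accuracy of one column. If the table is programmed as written, the listing will contain values that cannot be right, or bounds that are untrue. SAP 1 says the plan gives all the information needed for the analyses and requires an SAP amendment if analysis definitions change before database lock. A programmer's silent correction is therefore not the proper remedy.

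**Working it through.** **Inputs.** The row formulas and anchors come from SAP Table 4-1, the absence of a Day 0 from SAP 3.2.1, and the periods from SAP 3.2.2. The calendar is my assumption: dosing at 08:00 on 15 September 2020, which puts Day 140 on 1 February 2021. The sign of each result and the contradictions do not depend on that choice.

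**Checking my reading against the plan's own figures.** The table gives 23:59 as 23.98 hours: 23 + 59/60 = 23.983, which agrees. The periods add to 27 + 1 + 140 = 168 days, the stated duration. With no Day 0, Day n after dosing lies n - 1 days from dosing, and Day -n lies n days before it. Day 140 is therefore 139 days after dosing.

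**1. Start missing, end known.** Listed value: less than [24 × (D2 - D0) + (T2 - T0)] / 24 days.

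- *Ended Day -10 at 12:00.* [24 × (-10) + (12 - 8)] / 24 = -236/24 = -9.83. The listing shows less than -9.83 days, which is impossible.
- *True onset Day -20 at 08:00, ended Day 5 at 12:00.* Listed: [24 × 4 + 4] / 24 = 100/24 = 4.17. True: 20 + 4 + 4/24 = 24.17. The listing shows less than 4.17 days for an AE that lasted 24.17.

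**2. Both dates missing, AE resolved.** Listed value: less than Discharge - D0 = 139 days. For a true course from Day -20 to Day 138, the duration is 20 + 137 = 157 days, so the bound is false.

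**3. Both dates missing, AE ongoing.** Listed value: more than 139 days, whatever the onset.

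| True onset | Elapsed at Day 140 | Listed |
|---|---|---|
| Day 30 | 139 - 29 = 110 d | > 139 d |
| Day 100 | 139 - 99 = 40 d | > 139 d |
| Day 130 | 139 - 129 = 10 d | > 139 d |

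**4. Start month known, day missing.** This step applies only if such dates fall in the rows whose start is shown as fully blank.

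- *Start August 2020, ended 20 September at 08:00.* Listed as less than 5 days. Even an onset at the last moment of 31 August gives more than 19 days, so the bound contradicts the recorded month.
- *Start January 2021, ongoing, end missing.* Listed as more than 139 days. From 1 January to 1 February at most 31 days have elapsed.
- *Start November 2020, ended 20 November at 08:00.* Listed as less than 66 days (15 + 31 + 20). The real maximum is between 19 and 20 days, so this bound is loose but true.

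**The case against.** Several points on the other side are sound.

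- A reader might infer that every AE with a missing start is anchored to the dosing time. The documents do not say so. Screen failures are anchored to the Screening Visit, and the both-missing cases use the dosing date without a time.
- A reader might infer that the inequality for ongoing AEs is reversed. It is not. An ongoing AE is censored at discharge, so a greater-than sign is the right direction once an onset is accepted, as in the row above it where the onset is known. The AE may also go on to last longer than 139 days. The fault is that this minimum is unsupported when the onset is unknown; a less-than sign would be no better.
- A reader might infer that any known start month is contradicted. The November record shows otherwise. A conflict needs a start month before dosing with a known end, or a start month after dosing in an ongoing AE. It also depends on reading month-known dates as belonging to the blank-start rows. The introductory sentence, which covers partially missing dates, allows that reading but does not compel it.
- The two sets of rules often agree. For a completely unknown start, the classification rules also impute dosing unless that falls after the end date. Their stated purpose is classification, not duration.
- Duration is not an endpoint and is not summarised. The listings show dates as reported, so the missing onset is visible beside the duration, and the data evaluation meetings can discuss missing values.

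None of this removes the negative durations or the false upper bounds in steps 1 and 2, or gives the lower bound in step 3 any support. Visibility in the listing and review at a meeting soften the effect; they do not correct the rule.

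**Conclusion.** The point holds for dosed participants. Where the AE start date is missing, Table 4-1 can list a negative duration if the AE ended before dosing, a false upper bound if it began before dosing, and an unsupported lower bound if it is ongoing and undated. A contradiction with a known start month is possible but conditional on how the table is read. For AEs that truly began after dosing, the upper bounds are valid, though loose.

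The consequence is small: one column of the AE listing. A reader might infer that the secondary safety endpoint is affected, since it consists of treatment-emergent AEs and SAEs. It is not. Treatment-emergent status follows the separate start-date rules, the incidence tables do not use duration, and the bioequivalence analysis is untouched. The documents do not say how many AEs will lack a start day; in a single-centre study it is probably few. The worked records are constructed cases, not forecasts of the data.

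**What to change.** In Table 4-1, for dosed participants with a missing start day, compute every upper bound from the earliest possible onset instead of D0/T0. That is the first of the known start month or the Screening/consent date, whichever is later, taken at 00:00. Where the end time is also absent, count days inclusively, as the row for missing start and end times already does. State in the table that a start with a known month follows this rule.

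Taking consent on Day -28 for illustration, the Day -10 record becomes less than 18 + 12/24 = 18.5 days. The Day -20 to Day 5 record becomes less than 28 + 4 + 12/24 = 32.5 days, which covers the true 24.17. Provided recorded AEs do not start before consent, as the collection rule implies, every printed upper bound is then true and non-negative.

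For ongoing AEs with start and end missing, replace the lower bound with an entry of unknown, ongoing.

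Borrowing the start date imputed for classification would not be enough. For the Day -20 to Day 5 record that rule imputes dosing, and its fall-back is not triggered because the end is after dosing, so the result is 4.17 days again. A duration that rests on an onset imputed as dosing should not be printed as if it were exact.

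The cost is a few lines of SAP text and listing code, with no new data. Some upper bounds become looser and a few durations are listed as unknown.

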#### 4.3 Handling of repeated and unscheduled measurements

All repeated and unscheduled measurements will be presented in the listings. Repeated and unscheduled measurements will not be used for statistical analysis or summary tables, unless the repeated measurement was performed due to unreliable values/technical reasons, or the repeated measurement occurred prior to IMP administration and is defined as the 'Baseline'. The following general rules will apply to all repeated and unscheduled measurements:

- For repeated measurements obtained prior to the IMP administration, the latest reliable value (which may be scheduled or unscheduled) will be used in the calculation of descriptive statistics

- For repeated measurements obtained at any time point after dosing, the first reliable value of any repeated measurements will be used in the calculation of changes from Baseline and for the descriptive statistics.

#### **4.4 Interim analyses and data monitoring**

No formal interim analysis is planned for this study.

Two DEMs will be performed for this study prior to the final analysis. The purpose of these DEM reviews will be to review all protocol deviations, define the analysis sets as defined in [Section 3.5](#) and check the quality of the data. The reviews will also help decide how to manage problems in the participants' data (e.g. missing values and withdrawals).

Accepted deviations from planned time points will be described in the appropriate documents and included in the Study Master File. After the pre-analysis review, resolution of all issues, and documentation of all decisions (including inclusion into each of the analysis sets) at the final DEM, the database will be locked.

### **5 STUDY POPULATION CHARACTERISTICS**

#### **5.1 Subject disposition**

Participant screening and primary reason for screen failure will be summarized using the ES. The summary will include the following:

- Number of participants screened
- Number and proportion of participants rescreened
- Number and proportion of participants with screen failures (Not counting successfully rescreened participants)
- Number and proportion of screen failures by primary reason for screen failure (based on the later screening visit, in case of rescreen).

Disposition of analysis sets will be summarized using the ES. The summary will include the total number of participants in the ES, as well as the number and percentage of participants in each analysis set by treatment group. The percentages will be calculated based on the RS.

Study completion/discontinuation and primary reason for discontinuation will be summarized by treatment group and overall using the RS. The summary will include the following:

- Number and percentage of participants that started the study
- Number and percentage of participants completing the study
- Number and percentage of participants discontinuing the study
- Number and percentage of participants discontinuing the study by primary reason for discontinuation.

Participants that started the study are defined as participants that were randomized. Participants completing the study are those participants completing the SFU visit, i.e., the participant will be regarded as a completer if the SFU (Day 140) visit was completed.

Study discontinuation due to AEs will be summarized using the RS. The summary will present the number and percentage of participants who discontinued the study due to AE of the by treatment group and overall.

By-participant listings of participant disposition will be provided by treatment group using the ES, and will include the following:

- Study termination/completion status
- Date of informed consent
- Date of randomization
- Date and time of study medication administration
- Date of last contact
- Date of premature study termination for successfully screened participants dropping out of the study
- Date of screen failure for screen failure participants (based on the later screening visit in case of rescreen)
- Primary reason for premature study termination, as applicable
- Primary reason for screen failure, as applicable (based on the later screening visit in case of rescreen).

By-participant listings of study discontinuation will be presented by treatment group, using the RS. The listing will include the primary reason for discontinuation and the number of days since study medication administration.

By-participant listings of visit dates will be presented by treatment group using the FAS.

By-participant listings of participant who did not meet study eligibility criteria will be presented by treatment group, using the ES. The listing will include inclusion criteria that were not met and the exclusion criteria that were met. A glossary listing of inclusion and exclusion criteria will also be provided.

By-participant listings of participant inclusion in each analysis set will be presented by treatment group, using the ES.

## **5.2 Protocol deviations**

IPDs will be identified and classified by the deviation types listed in the IPD specification document.

IPDs will be summarized by treatment group and overall using the RS. The summary will include the following:

- Number and percentage of participants with no IPDs
- Number and percentage of participants with at least one IPD
- Number and percentage of participants by type of protocol deviation

By-participant listings of IPDs as identified in the DEMs will be provided by treatment group using the RS. This will include deviation type, deviation description, and whether the deviation led to exclusion from the PK-PPS. Similar listings and tables will be produced for IPDs related to COVID-19.

